### Schedule of Assessments

Schedule	Preop	Op	DC	3 mo $\pm$ 4 wks	6 mo $\pm$ 4 wks	1 yr $\pm$ 4 wks	2 yr $\pm$ 6 wks	5yr -2 wks+ 180 days	6yr $\pm$ 90 days	7yr $\pm$ 90 days	8yr $\pm$ 90 days	9yr $\pm$ 90 days	10yr $\pm$ 180 days	Unscheduled
Days	-	-	-	64-120	155-211	338-394	689-773	1812-2006	2101-2281	2466-2646	2831-3019	3196-3376	3471-3831	-
Inclusion/Exclusion	✓	-	-	-	-	-	-	✓	-	-	-	-	-	-
Informed Consent	✓	-	-	-	-	-	-	✓	-	-	-	-	-	-
Demographics/Med History	✓	-	-	-	-	-	-	-	-	-	-	-	-	-
Clinical Evaluation (HHS)	✓ a	-	-	✓ a	✓ a	✓ a	✓ a	✓	-	✓	-	-	✓	✓ a
Radiography	✓ a	-	✓ a	✓ a	✓ a	✓ a	✓ a	✓		✓			✓	✓
Metal Ion Testing (Whole Blood)	✓	-	-	✓	✓	✓	✓	✓	-	✓	-	-	✓	✓
HOOS Subject Questionnaire	✓ a	-	-	✓ a	✓ a	✓ a	✓ a	✓	-	✓	-	-	✓	✓ a
Adverse Events	-	✓	✓	✓	✓	✓	✓	✓	✓	✓	✓	✓	✓	✓
End of Study	-	-	-	-	-	-	-	-	-	-	-	-	✓ c	-
Retrospective Demographics/Med History Data Collection b	✓	✓	✓	✓	✓	✓	✓	-	-	-	-	-	-	-
Retrospective Clinical Evaluation (HHS) b	✓			✓	✓	✓	✓							
Retrospective HOOS b	✓			✓	✓	✓	✓							
Retrospective Adverse Event Data Collection b	✓	✓	✓	✓	✓	✓	✓	-	-	-	-	-	-	-
Retrospective Radiography Data Collection b	✓	✓	✓	✓	✓	✓	✓	-	-	-	-	-	-	-

a - For Investigational subjects only

b - Control subjects only

c - An end of study form will be completed for all subjects at the 10 year visit if not completed prior

Statistical Analysis Plan	
A Consecutive Series Pilot Study Evaluating the Safety and Effectiveness of a New Hard-on-Hard Total Hip Replacement System in Patients with Non-inflammatory Arthritis with a Standard THA Metal Ion Control Group	Number: 2011-ODHH166
	ST: 1040
	Version: V1.0 26-Nov-2018
	Page: 6 of 13

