### 5.3 Interim Analysis

Interim analyses will be conducted post-operatively after all subjects have completed 5 year and 7 years visits. The focus of these analyses will be on safety and efficacy.

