#### Revision Data

- Any subject classified as lost-to-follow-up, deceased or withdrawn will be censored in the survival analysis on the date which it occurs. If a device-related revision occurs this will be considered a device failure. If none of the above occur before the end of the study the subject will be censored on end of study visit/ date of interim analysis.

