### 6.9.1 Device-Related Revisions

The Kaplan-Meier product limit survival estimates will be presented at 6-months, 2-years, 5-years, 7-years and 10-years post-op along with the associated 95% confidence intervals. The event of interest will be device-related revisions. Subjects who do not have device-related revision will be censored either at the time-point being analysed i.e. 5-years at the 5-year interim analysis etc. or at the time they discontinue from the study for

Statistical Analysis Plan	
A Consecutive Series Pilot Study Evaluating the Safety and Effectiveness of a New Hard-on-Hard Total Hip Replacement System in Patients with Non-inflammatory Arthritis with a Standard THA Metal Ion Control Group	Number: 2011-ODHH166
	ST: 1040
	Version: V1.0 26-Nov-2018
	Page: 11 of 13

any other reason i.e. lost to follow-up. This analysis will be presented by treatment (control/ R3 ODH-ODH).

The Kaplan Meier Survival plot will also be presented at 12 months both overall and by device type.

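### SAP 6.4 and 6.9.1 give conflicting censoring dates for unrevised subjects in the primary Kaplan-Meier analysis, and the two rules can give different 10-year results

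*SAP*

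**What the plan says.** SAP 6.4, under Revision Data, deals first with early leavers: "Any subject classified as lost-to-follow-up, deceased or withdrawn will be censored in the survival analysis on the date which it occurs". For a subject who neither leaves early nor has a device-related revision, it says "the subject will be censored on end of study visit/ date of interim analysis".

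SAP 6.9.1 describes the same analysis ("The event of interest will be device-related revisions"). It says that subjects without such a revision "will be censored either at the time-point being analysed i.e. 5-years at the 5-year interim analysis", with the same pattern implied for later analyses, or at the time they discontinue. Product-limit "survival estimates will be presented at 6-months, 2-years, 5-years, 7-years and 10-years post-op along with the associated 95% confidence intervals".

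The two sections agree on early leavers. They disagree on subjects who stay in the study unrevised, and nothing says which section prevails.

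Two other provisions matter:
- **Final visit.** The Schedule of Assessments footnote says "An end of study form will be completed for all subjects at the 10 year visit if not completed prior". The schedule gives that visit a window of 180 days either side, listed as days 3471 to 3831.
- **Interim timing.** SAP 5.3 says "Interim analyses will be conducted post-operatively after all subjects have completed 5 year and 7 years visits".

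**The concern.** Device-related revision is a primary endpoint, and censoring dates are part of the definition of its analysis. Two programmers could each follow the SAP faithfully and produce different risk sets. Left open, the choice would be made after the data are visible.

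The final visit can take place before the 10-year anniversary. Under 6.4, a subject seen on day 3471 leaves the risk set that day. Under 6.9.1, the same subject counts as revision-free until 10 years, with up to about 180 days in which nobody observed the hip. The interim-analysis date in 6.4 has a similar weakness. The interim waits for every subject to complete the visit, so a subject seen early is given follow-up beyond the last contact.

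With about 20 investigational subjects, survival of 100% is a plausible result. The number at risk then becomes the main guide to how much evidence supports it, and that number depends on the rule chosen.

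**Working it through.** **Inputs from the documents.** 20 ODH-ODH subjects (SAP 5.1); 10-year window of days 3471 to 3831 (schedule); the two censoring rules above. The documents give no revision rate, expected survival or distribution of visit dates, so those below are assumptions.

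**Reproducing the window.** With target day = 365 × years + 1, the 10-year target is 365 × 10 + 1 = 3651. Then 3651 − 180 = 3471 and 3651 + 180 = 3831, as printed. Taking 10 years as 10 × 365.25 = 3652.5 days, the window opens 3652.5 − 3471 = 181.5 days early. The difference from 180 is immaterial.

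**Number at risk at 10 years, no revisions.** With visits evenly spread, the share of final visits before day 3652.5 is 181.5 / 360 = 0.504. With 20 evenly spaced visits, 10 fall after that day. So 10 of 20 are at risk under 6.4 and 20 of 20 under 6.9.1. Estimated survival is 100% under both.

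**Estimate with one revision.** With a single event, S(10 y) = 1 − 1/r, where r is the number at risk on the event day. Put the 19 unrevised subjects' visits at equal steps of 360 / 18 = 20 days from day 3471. Under 6.4, r = 20 minus the number of visits before the event; under 6.9.1, r = 20. The 95% intervals are log-log.

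| Revision on day | r under 6.4 | S(10 y) under 6.4 (95% CI) | S(10 y) under 6.9.1 (95% CI) |
|---|---|---|---|
| before 3471 | 20 | 95.0% (69.5 to 99.3) | 95.0% (69.5 to 99.3) |
| 3500 | 18 | 94.4% (66.6 to 99.2) | 95.0% (69.5 to 99.3) |
| 3561 | 15 | 93.3% (61.3 to 99.0) | 95.0% (69.5 to 99.3) |
| 3600 | 13 | 92.3% (56.6 to 98.9) | 95.0% (69.5 to 99.3) |
| 3640 | 11 | 90.9% (50.8 to 98.7) | 95.0% (69.5 to 99.3) |
| after 10 years | – | 100% | 100% |

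For example, at day 3640 nine visits (days 3471 to 3631) have already happened, so r = 20 − 9 = 11 and S = 10/11 = 90.9%.

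The spread of visits matters. If all 19 visits fall between days 3471 and 3640, a revision on day 3561 gives 90.0% against 95.0%. If all fall after 10 years, both rules give 95.0%.

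**How often the estimates differ.** Simulation with n = 20, visits uniform over the window, a constant hazard and no earlier dropout:

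| Assumed 10-year revision risk | Trials in which S(10 y) differs |
|---|---|
| 5% | about 3% |
| 10% | about 6% |
| 20% | about 10% |

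Where the estimates differed, the mean gap was about 2 percentage points. Averaged over all simulated trials it was about 0.06 to 0.22 points, with 6.9.1 never the lower of the two.

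**Interim analyses.** When every interim date was set later than 5 years, censoring there or at 5 years gave identical S(5 y) in all 3,000 simulated trials. Time after a landmark does not enter the estimate at that landmark. It only lengthens the curve and the follow-up shown beyond it.

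**The case against.** The strongest reply is that this changes little. A reader might infer that the two rules always give different 10-year survival. They do not: with no revision, with every revision before day 3471, or with every revision after 10 years, the estimates are the same. The day 3640 figure also lies near the end of the sensitive interval, where the gap is widest, so it is not typical. Both points stand.

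A reader might also infer that the interim-analysis date or the nominal time-point credits revision-free status that nobody checked, and so inflates survival generally. The documents do not support that. Investigators report revisions within 24 hours of awareness (Protocol 17.3), the sponsor is told immediately when one is planned (Protocol 18.0), and adverse events are assessed by telephone at 6, 8 and 9 years (Protocol 14.0). Up to the final visit, revision reporting is continuous. The criticism has force for time after the final visit under 6.9.1. For the interim date, what remains is follow-up shown beyond last contact, not a shifted 5-year estimate.

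It can also be said that time-point means the study visit, so that 6.4 merely supplies the date for 6.9.1. That does not remove the conflict, because 6.9.1 explains its own term: "censored either at the time-point being analysed i.e. 5-years at the 5-year interim analysis etc". That is an elapsed time, not a visit date.

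Finally, this is a 25-subject pilot. Protocol 22.3.1 makes the extension analyses descriptive, and no revision threshold is stated that a decision would turn on. That limits the severity but does not make either rule the agreed one.

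**Conclusion.** The contradiction is real and concerns a primary endpoint. Its numerical effect is conditional and usually small. At 10 years the number at risk can differ by about a factor of two (10 against 20) even with no revisions. The survival estimate and its interval differ only if a revision falls between day 3471 and 10 years after another subject's final visit. For one revision among 20 with evenly spread visits, the gap runs from 0.6 points (day 3500) to 4.1 points (day 3640).

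These sizes rest on assumed visit dates, assumed revision risks and no loss before the 10-year window. They illustrate the effect and do not predict it. The 5-year result holds for interim dates later than each subject's 5-year point. Severity is minor to moderate.

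**What to change.** State one rule, in the same words, in SAP 6.4 and 6.9.1:
- Censor each unrevised subject at the last date on which revision status was known in the study data: a clinic visit, a telephone contact, or a family-doctor contact where the subject consented and the contact was recorded. At 10 years this is normally the end-of-study visit that 6.4 already names.
- Remove the nominal time-point and the date of interim analysis as censoring dates.
- Print the number at risk beside each Kaplan-Meier estimate.

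The cost is SAP wording. Visit and telephone contacts are already scheduled. Family-doctor contacts are recorded in source documents (Protocol 16.0), so it should be confirmed that their dates reach the analysis data.

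There are two downsides. Fewer subjects will be at risk at 10 years, and the interval will be wider when a revision falls late. There may also be slight downward bias, because revisions can be reported between contacts while unrevised subjects are censored back to their last contact. The SAP should acknowledge this.

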#### HHS

- Total HHS score will be calculated as per the specific version instructions.
- Absolute change in Total HHS Score = Score at visit – Score at baseline (pre-op).

#### HOOS

- HOOS domain scores will be calculated as per the specific version instructions
- Absolute change in HOOS domain Score = Score at visit – Score at baseline (pre-op).

## 6.5 Baseline Data

Baseline data to be summarised for all populations:

- Operated Side (Left/ Right/ Bilateral)
- Demographics (to be summarised by subjects) - age, sex, height, weight, BMI, ethnicity

Statistical Analysis Plan	
A Consecutive Series Pilot Study Evaluating the Safety and Effectiveness of a New Hard-on-Hard Total Hip Replacement System in Patients with Non-inflammatory Arthritis with a Standard THA Metal Ion Control Group	Number: 2011-ODHH166
	ST: 1040
	Version: V1.0 26-Nov-2018
	Page: 10 of 13

- Medical History - Primary Diagnosis, other co-morbidites, tobacco and alcohol use
- Operative data – Surgical approach, total operative/ anesthesia time, total blood loss, bone graft used, antibiotic prophylaxis used, DVT prophylaxis used, head reducer used, drains used, cables or wires used,

## 6.6 Disposition Data

The following disposition data will be summarised for all populations

- Number of subjects/ hips in each analysis population (present both if any bilateral subjects are enrolled)
- The number of subjects/ hips that attend each study visit.
- Reason for study discontinuation
- The dates of first subject first visit and last subject last visit will be included as a footnote

## 6.7 Protocol Deviations

All protocol deviations will be listed including the deviation date, description of the deviation and whether this led to the subject being removed from the PP population.

## 6.8 Multiplicity

No adjustments for multiplicity are planned for this study.

## 6.9 Analysis of Primary Endpoints

All primary endpoints are assessed using the safety population

### 6.9.1 Device-Related Revisions

The Kaplan-Meier product limit survival estimates will be presented at 6-months, 2-years, 5-years, 7-years and 10-years post-op along with the associated 95% confidence intervals. The event of interest will be device-related revisions. Subjects who do not have device-related revision will be censored either at the time-point being analysed i.e. 5-years at the 5-year interim analysis etc. or at the time they discontinue from the study for

Statistical Analysis Plan	
A Consecutive Series Pilot Study Evaluating the Safety and Effectiveness of a New Hard-on-Hard Total Hip Replacement System in Patients with Non-inflammatory Arthritis with a Standard THA Metal Ion Control Group	Number: 2011-ODHH166
	ST: 1040
	Version: V1.0 26-Nov-2018
	Page: 11 of 13

any other reason i.e. lost to follow-up. This analysis will be presented by treatment (control/ R3 ODH-ODH).

The Kaplan Meier Survival plot will also be presented at 12 months both overall and by device type.

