3.0 Outcome Measures

3.1 Primary Outcome Measures

- Primary safety will be assessed by the incidence of device related revision, adverse events and metal ion measurements.
- Adverse events will be documented at the intraoperative and all post-operative evaluation intervals. The incidence of surgery-related and device-related events such as squeaking, liner fracture, device revision, malfunction, migration, subluxation, dislocation, loosening, nerve damage, deep infection, deep vein thrombosis, pulmonary embolism, or bone breakage/fracture will also be collected. Any adverse events with an unknown association with the surgery or device will also be collected.
- For both investigational and control subjects, metal ions will be measured in whole blood, including Co, Cr, Ni, Ti, Zr, Nb, Mo, V and aluminum (Al) ion levels, preoperatively, 3 month, 6 month, 1 year, 2 years, 5 years, 7 years and 10 years post-operatively.

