18.0 Device Failure leading to revision

In the short term, THA failure can occur due to infection, dislocation, instability, and/or subject experiencing severe pain due to various causes. Reduced mobility alone, is typically not a predominant factor in prompting revision surgery. In the longer-term, aseptic loosening and/or severe pain may become a determining factor as to whether to proceed with device revision. Reasons for removal are not limited to these circumstances alone.

The Sponsor should be notified immediately when a revision is planned. The Sponsor or its designee will provide an explant retrieval kit and the site will return any revised components for retrieval analysis according to provided instructions. Any explanted devices must be logged on the device accountability log when explanted and shipped to the Sponsor or its designee. Blood will be collected for metal ion analysis and radiographs taken prior to the revision procedure as per an unscheduled visit on the study visit schedule. Patients who have undergone revision surgery will be withdrawn from the study and no additional follow-up visits will occur.

Explanted components are to be sterilized by steam autoclave or other appropriate sterilization method according to the Institution's standard sterilization procedures. Only properly packaged explants should be shipped, and the Sponsor notified before any shipment. If possible, the Sponsor will collect histological (bony in-growth quality, bone quality, response to potential wear debris, etc.) and metallurgical (metal wear, deformation, cracking, corrosion, etc.) information from explants, and this information will be reported in annual safety reports. For all explants, the Investigator must record and forward a description of intra-operative findings including: 1) presence of wear debris, 2) what types of components are being replaced, 3) and intraoperative findings relating to the device failure. It should be noted that the Sponsor is not always able to retrieve known explants.

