22.4 Adverse Events

Time course distribution of Adverse Events for the safety population will be tabulated. Analysis of revision status will be done using a test of proportion such as Binomial test and Chi-square test unless otherwise noted. Additionally, the safety of R3 ODH-ODH will be assessed by analyzing the revision rate at 6 months, two years, 5 years, 7 years and 10 years post-operatively as well as by applicable operative and post-operative adverse events (device related or otherwise). Kaplan-Meier estimates will be used to analyze the survivorship of the prosthesis. For survivorship analyses, revision of one or more components will be defined as failure.

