#### 6.3 Handling of Missing, Incomplete and Repeat Data

- **Revision data** - If a subject has a revision at any point during the study, for purposes of calculating the revision rate by a particular visit then the fact that a revision has occurred will be carried forward to all the following visits.
- **HHS/ HOOS** – If any individual HHS/ HOOS responses are missing at a post-baseline visit then the data will be input from the previous assessment using the Last Observation Carried Forward (LOCF) method. If baseline is the only previous data point then no implementation methods should be used, baseline data should not be carried forward. If all HHS/ HOOS responses are missing at a post-baseline visit (including if a subject has discontinued from the study) then all missing dimension scores should be carried forward using the LOCF method as above, with no carrying forward of baseline values.

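### The SAP's Kaplan-Meier analysis counts only device-related revisions as failures, so it can overstate implant survivorship as protocol 22.4 defines it

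*SAP*

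**What the plan says.** **Failure event.** Protocol 22.4 prescribes Kaplan-Meier for survivorship of the prosthesis and defines the event: "For survivorship analyses, revision of one or more components will be defined as failure". SAP 6.9.1 uses a different one: "The event of interest will be device-related revisions". The Revision Data part of SAP 6.4 agrees with 6.9.1: "If a device-related revision occurs this will be considered a device failure". The SAP plans no second survivorship analysis on all revisions.

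**Primary outcome.** Protocol 3.1 uses the narrower term: "Primary safety will be assessed by the incidence of device related revision, adverse events and metal ion measurements". SAP 4.1 repeats it.

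**Revision rate.** SAP 6.3 has a carry-forward rule with no condition on cause. It begins: "If a subject has a revision at any point during the study, for purposes of calculating the revision rate by a particular visit".

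**After a revision.** Protocol 18.0 states: "Patients who have undergone revision surgery will be withdrawn from the study and no additional follow-up visits will occur". SAP 6.4 censors withdrawn subjects on the date of withdrawal.

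**Event-free subjects.** SAP 6.9.1 says: "Subjects who do not have device-related revision will be censored either at the time-point being analysed". SAP 6.4 says instead that "the subject will be censored on end of study visit/ date of interim analysis".

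**The concern.** Revision is a primary safety endpoint, and a survivorship percentage is a natural headline figure for a new bearing. Protocol 18.0 lists infection, dislocation, instability and severe pain as reasons a hip replacement can fail in the short term. Some of these could be judged not device-related, and neither document says what device-related means for a revision or who decides. Under the SAP, a hip revised for such a reason leaves the analysis as a censored non-failure. The survivorship figure then depends on an unspecified judgement, and any departure from the protocol's figure favours the device.

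Two smaller problems sit alongside:

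- The revision rate by visit under SAP 6.3 and the Kaplan-Meier estimate under 6.9.1 could count different events.
- SAP 6.9.1 and 6.4 censor event-free subjects on different dates, and neither rule is tied in general to the last date on which implant status was known. For losses, protocol 16.0 defines loss by a missed visit followed by failed contact, so the loss is dated after status was last known. The SAP does not say which date to use.

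**Working it through.** The documents give no revision rate, survivorship target or expected event count, so there is no planned figure to reproduce. The size below is illustrative.

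**Inputs from the documents.** 20 ODH and 5 control subjects (SAP 5.1); estimates by treatment up to 10 years (SAP 6.9.1); year-10 visit window day 3471 to 3831 (both schedules).

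**Assumed.** The number, timing and cause of revisions; all other subjects event-free to 10 years; a version with only 15 ODH subjects contributing.

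**Step 1: direction.** The product-limit estimate multiplies (1 − 1/r) over failures, where r is the number at risk just before each one. A revised subject leaves the risk set at revision under both definitions. The only difference is that an other-cause revision contributes (1 − 1/r) under protocol 22.4 and a factor of 1 under the SAP. Hence

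S(protocol) = S(SAP) × product of (1 − 1/r) over other-cause revisions.

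The product is at most 1, so the SAP estimate is never the lower of the two. They are equal if there are no other-cause revisions.

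**Step 2: size.**

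| Assumed revisions | n | Protocol 22.4 | SAP 6.9.1 | Difference (points) |
|---|---|---|---|---|
| 1 other-cause | 20 | 19/20 = 95.0% | 100% | 5.0 |
| 1 device-related, 1 other | 20 | 18/20 = 90.0% | 19/20 = 95.0% if the device-related one is first, 18/19 = 94.7% if second | 5.0 or 4.7 |
| 1 other, then 2 device-related | 20 | 17/20 = 85.0% | 18/19 × 17/18 = 89.5% | 4.5 |
| 1 device-related, 2 others | 20 | 17/20 = 85.0% | 95.0%, 94.7% or 17/18 = 94.4%, by order | 10.0, 9.7 or 9.4 |
| 1 other-cause | 15 | 14/15 = 93.3% | 100% | 6.7 |
| 1 device-related, 1 other | 15 | 13/15 = 86.7% | 14/15 = 93.3% or 13/14 = 92.9% | 6.7 or 6.2 |
| 1 other-cause, control arm | 5 | 4/5 = 80.0% | 100% | 20.0 |

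With 20 subjects, each other-cause revision is worth about 4.5 to 5 points.

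**Step 3: precision.** With complete follow-up the estimate is a simple proportion. Exact (Clopper-Pearson) 95% intervals are 68.3% to 98.8% for 18/20 and 75.1% to 99.9% for 19/20. They overlap heavily.

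**Step 4: censoring of event-free subjects.** The two SAP rules give the same 10-year figure unless a revision falls between another subject's early in-window final visit and the nominal date, a gap of up to 180 days (3651 − 3471). Take one failure at day 3600 and k of the 20 with a final visit at day 3471:

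- SAP 6.9.1 (nominal date): 1 − 1/20 = 95.0% for any k.
- SAP 6.4 (visit date): 1 − 1/(20 − k), which is 94.4% for k = 2 and 93.3% for k = 5.

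**Step 5: date of loss.** Take one failure at 4 years and m of the 20 last seen at 2 years. Censoring at last contact gives 1 − 1/(20 − m): 94.7%, 94.4% and 94.1% for m = 1, 2 and 3. Dating the loss at the missed 5-year visit gives 95.0%.

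**The case against.** The strongest defence is that the SAP event comes from the protocol. Protocol 3.1 names device-related revision as a primary outcome, and SAP 6.9.1 carries that term in its heading, so the curve is labelled for what it is. On this view the protocol holds two definitions, and the fair charge is that one analysis is missing. That supports keeping a device-related curve. It does not supply the 22.4 analysis, because 3.1 sets an incidence outcome and 22.4 is the only place that defines failure for survivorship.

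Other points, and what stands of each:

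- **22.4 fixes which components count and does not mention cause.** True; the any-cause reading rests on the absence of a restriction. It is still the natural reading, and nothing in 22.4 supports a narrower one.
- **SAP 6.3 is a missing-data rule, and SAP 6.9 specifies no revision-rate table.** This stands in part: the two results could differ, not necessarily would. Protocol 22.4 does call for revision rates at the same time-points.
- **Other-cause revisions would be visible elsewhere,** on the revision and adverse event forms, in the adverse event summaries and in the reasons for discontinuation. True, but none of these corrects the survivorship percentage.
- **The censoring effects are small, and the loss example is debatable.** Both hold. The day-3600 example moves the estimate by 0.6 to 1.7 points. A subject who completed year 2 and never consented to the extension need not be classed as lost at year 5.
- **This is a 25-subject pilot with descriptive extension analyses and no survivorship target.** True, and it limits what any estimate here can show. It does not excuse computing a primary safety result on an event other than the one the protocol defines.

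**Conclusion.** The concern holds. Followed as written, the SAP does not deliver the survivorship analysis that protocol 22.4 requires. The direction is certain and does not depend on the assumptions. The size does: it depends on how many revisions are judged not device-related, and it is zero if there are none. The larger differences shown for 15 ODH subjects and for the control arm simply reflect fewer subjects at risk. Nothing here turns on statistical significance. The mismatch with SAP 6.3 and the two censoring rules are real but secondary, and worth settling in the same revision.

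**What to change.** 1. In SAP 6.9.1 and 6.4, make revision of any component for any cause the Kaplan-Meier failure event. This follows protocol 22.4 and matches SAP 6.3.
2. Report device-related revision as a second, separately labelled curve for protocol 3.1. State how a revision is classified as device-related, who decides, and that other-cause revisions are censored in that curve.
3. Replace the two rules for event-free and lost subjects with one: censor at the last date on which implant status was documented, whether by visit, telephone contact, GP contact or death. GP contact should count only where consent allows it and implant status was actually recorded, since protocol 16.0 describes that contact as a check on general health.

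The cost is SAP wording and one extra curve; no new data are needed. The downside for the sponsor is that the stated survivorship may be less favourable.
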